8.9.3 Actual Cumulative Dose

The actual cumulative dose of RP-1664 is defined as the sum of all actual doses administered taking into consideration of any dose change during the study treatment exposure

8.9.4 Actual Dose Intensity

The actual dose intensity (ADI) is defined as the actual cumulative dose during a cycle, calculated as:

[figure not shown]
$$RP-1664 \ ADI \ (mg/cycle) = \frac{\textit{Actual Cumulative Dose (mg)}}{\frac{\textit{Duration of exposure (days)}}{\textit{planned cycle length (days/cycle)}}}$$

[figure not shown]
8.9.5 Relative Dose Intensity

[figure not shown]
The Relative Dose Intensity is defined as the percent dose taken in a cycle, derived as the ADI divided by Planned Dose Intensity (PDI). The PDI is derived as the initial dose of the study drug multiplied by planned number of dosing days per cycle according to the protocol at the start of the planned dose regimen.

Details of study treatment exposure will be listed for Safety Population and swimmer plot for duration of treatment for individual participants by dose level and dose schedule will be presented.

[figure not shown]

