S	Expand cohort at same dose
S1 to MTD or tolerated and	Up to 75% increases until MTD or tolerated
pharmacologically active dose	and pharmacologically active dose

Evaluation of the PK data after at least 6 participants, with sufficient data to derive PK parameters, may trigger adjustment of the daily dosing frequency of RP-1664 to allow for twice-daily (BID) dosing. BID dosing may be initiated based on observed participant outcomes and PK parameters such as, but not limited to, t1/2 is < 12 hours or the C_{max} : C_{min} ratio is > 10. Any decision to move from QD to BID dosing during the trial will be made after consultation with the SRC. If BID dosing is initiated, the Sponsor in agreement with SRC, can elect to continue or cease enrollment in QD dosing cohorts based on available data.

Additional treatment schedules, including daily dosing, 3 days on/4 days off, 1 week on/1 week off, or 2 weeks on/2 weeks off may also be explored to mitigate AEs and/or improve efficacy. If an additional schedule is tested, the starting dose of RP-1664 may be as high as the highest total daily dose that cleared DLT evaluation. The decision to test one or more of these schedules and set the starting dose level will be agreed upon by the SRC and will take into consideration all available safety, efficacy, pharmacodynamic, and PK data.

The food effect portion of the trial will be conducted at selected centers and may start at Dose Level 3 or once Dose Level S is reached. The fasting recommendation for RP-1664 in the general trial population may be revised to allow dosing with food after at least 4 participants have been evaluated in the food effect portion of the trial.

Expansion cohorts may be opened if at least one safe dose and schedule at which clinical activity is identified and agreed upon by the SRC. Up to 20 efficacy evaluable participants in each expansion cohort can be enrolled to further evaluate the safety, PK, pharmacodynamic, and preliminary efficacy of RP-1664 at the selected dose level(s). Enrollment in expansion cohorts may be limited to specific tumor types and/or genomic profiles based on assessment of clinical activity by the Sponsor in the dose escalation portion and other emerging preclinical, translational, and clinical data external to the trial.

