4.2 Study Procedure and Assessment

The trial will consist of a Pre-Screening Period (within 6 months from time of the Screening/Main Informed Consent Form [ICF] signature, to confirm molecular eligibility), Screening Period, Treatment Period (including PK evaluation period starting at cycle 0 Day 1, and continuing in 21- or 28- Day cycles), an End of Treatment (EOT) Visit (occurring within 7 days after the last dose of trial treatment), a Safety Follow-up Visit (occurring within 30 days \pm 14 days after the last dose of trial treatment), and a Survival Follow-up Period (survival follow-up assessments will be done every 90 days [\pm 14 days] after the date of treatment discontinuation until the end of trial [for up to 6 months after EOT] unless the participant

withdraws consent to the trial, the trial is terminated, the participant dies or is lost to follow-up), The end of Trial is defined as the date of the last visit (including all follow-up visit) of the last participant in the trial.

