8.9.2 Dose Reduction

Dose reduction is defined as 1) decreased in the total daily dose level or, 2) a decrease in the number of consecutive day (e.g., from 2 weeks on/1 week off to 3 days on/4 days off) or weeks (e.g. 2 weeks on/1 week off to 2 weeks on/2 weeks off).

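### Dose intensity is defined per cycle although cycles last 21 or 28 days, and the SAP does not say which cycle length or exposure window applies to RDI after a schedule change

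*SAP*

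**What the plan says.** - **ADI (SAP 8.9.4).** "The actual dose intensity (ADI) is defined as the actual cumulative dose during a cycle". The formula divides cumulative dose by the number of planned cycle lengths that fit into the duration of exposure. It has a single planned cycle length and does not say whether that is the starting or the current one. Duration of exposure is not defined there. The nearest definition is duration of treatment in SAP 8.9.1, which ends at the last dose date for participants who have discontinued.
- **PDI and RDI (SAP 8.9.5).** RDI is ADI divided by PDI. "The PDI is derived as the initial dose of the study drug multiplied by planned number of dosing days per cycle", fixed "according to the protocol at the start of the planned dose regimen". PDI is not divided by time.
- **Cycle length.** SAP 4.2 has treatment "continuing in 21- or 28- Day cycles". In the schedules of activities (SAP 14.1.1), 2 on/1 off, 3 days on/4 days off and daily dosing use 21-day cycles (Tables 1, 3 and 5). The 1 on/1 off and 2 on/2 off schedules use 28-day cycles (Tables 7 and 9).
- **Schedule changes.** SAP 8.9.2 gives a change from "2 weeks on/1 week off to 2 weeks on/2 weeks off" as an example of a dose reduction. The protocol synopsis (section 1.1) allows schedule changes within a participant to manage adverse events.
- **Reporting.** SAP 8.9 summarises exposure by dose level and schedule, and overall, for the whole treatment period and by cycle.

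**The concern.** A dose intensity should measure drug per unit of time. Here the unit is a cycle, and a cycle is not a fixed length of time in this trial. Two regimens that deliver different amounts per week can show the same ADI. A participant who changes to a longer cycle with the same number of dosing days can show an unchanged RDI, although the SAP itself calls that change a dose reduction. Because two inputs to the formula are left open, two programmers following the SAP could report values on opposite sides of 100% for the same participant.

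A primary objective is to define a tolerated dose and schedule. ADI and RDI are the summaries a reader would turn to when asking how much of the planned drug was actually taken on each schedule.

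**Working it through.** The SAP gives no numerical RDI to reproduce, so the check applies its formulas directly. Let D be the daily dose in mg, and assume every planned dose is taken. The exposure clock starts with Cycle 1, because SAP 8.9 excludes Cycle 0.

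ADI = cumulative dose / (exposure days / cycle length). PDI = D × planned dosing days per cycle. RDI = ADI / PDI.

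**1. Planned dose by schedule**

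| Schedule | Dosing days / cycle length | Per cycle | Per week |
|---|---|---|---|
| 2 on/1 off | 14 / 21 | 14D | 14/21 × 7 = 4.67D |
| 2 on/2 off | 14 / 28 | 14D | 14/28 × 7 = 3.50D |
| 1 on/1 off | 14 / 28 | 14D | 14/28 × 7 = 3.50D |
| 3 days on/4 off | 9 / 21 | 9D | 9/21 × 7 = 3.00D |
| Daily | 21 / 21 | 21D | 7.00D |

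The first three rows agree per cycle. Per week, 3.50/4.67 = 75%.

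**2. One full cycle after a change from 2 on/1 off to 2 on/2 off.** PDI stays at 14D.
- Length 28: ADI = 14D/(28/28) = 14D, so RDI = 100%.
- Length 21: ADI = 14D/(28/21) = 10.5D, so RDI = 75%.

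**3. Whole period: two full cycles of 2 on/1 off, then two full cycles of 2 on/2 off.** Cumulative dose is 4 × 14D = 56D, over 2 × 21 + 2 × 28 = 98 days.
- Length 28: 56D/(98/28) = 16D, so RDI = 114%.
- Length 21: 56D/(98/21) = 12D, so RDI = 86%.

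**4. Exposure ended at the last dose date.**
- The participant in step 3 loses the final 14 off days, leaving 84 days. Length 28: 56D/(84/28) = 18.67D, so RDI = 133%. Length 21: 56D/(84/21) = 14D, so RDI = 100%.
- A 2 on/1 off participant with no change of any kind, who stops after one cycle, has 14D over 14 days: 14D/(14/21) = 21D, so RDI = 150%.

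**5. Reductions that RDI does register over full cycles.**
- A change from 2 on/1 off to 3 days on/4 off: 9D/14D = 64%.
- An illustrative 25% cut in daily dose on an unchanged 2 on/1 off schedule: 10.5D/14D = 75%.

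**6. The same cases in mg/week, with the last off period counted.** PDI = 4.67D per week.
- Reduced cycle: 14D/4 weeks = 3.5D, so RDI = 75%.
- Whole period: 56D/14 weeks = 4.0D, so RDI = 86%.
- One complete 2 on/1 off cycle: 14D/3 weeks = 4.67D, so RDI = 100%.

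**7. Changing the unit alone is not enough.** With 84 days, 56D/12 weeks = 4.67D, so the switch example still gives RDI = 100%. The exposure window has to be defined as well.

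**The case against.** The strongest reply is that SAP 8.9.5 already ties PDI to the starting regimen. If the cycle length in SAP 8.9.4 is tied to it too, RDI over full cycles is algebraically the same as the mg/week ratio: 75% and 86% in the example. On that reading one clarifying clause would repair RDI. This stands as far as it goes. However, the SAP does not contain that clause. Because exposure is also summarised by cycle, using each cycle's own length is at least as natural a reading. The clause would not settle the exposure window, nor make ADI comparable across schedules.

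It is also fair that schedules are shown separately, so a reader can see which is which. Only the overall column mixes 21- and 28-day units, and for ADI that column pools different dose levels in any case. Pooling does make sense for RDI, where each participant is scaled to their own plan, so its definition matters most there.

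Three stronger inferences are tempting, and the documents do not support them:
- *That RDI misses dose reductions in general.* It does not. Over full cycles it falls for a lower daily dose and for a change to 3 days on/4 off. The cycle-length problem is shown for a change from a 21-day to a 28-day cycle with 14 dosing days in each.
- *That such reductions go unreported.* SAP 8.9.2 classes the schedule change as a dose reduction, SAP 12.2 tabulates related adverse events leading to reduction, and SAP 8.9.5 lists exposure by participant.
- *That twice-daily participants will score 200%.* That requires reading the initial dose in PDI as one administration. The escalation table is in daily mg, and SAP 4.1 and 8.9.2 speak of total daily dose. This is a wording ambiguity only.

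**Conclusion.** The point holds with limited scope. At the same daily dose, three schedules show identical mg/cycle while their weekly dose differs by 25%. For the SAP's own example of a schedule reduction, RDI is 100% or 75% for a full reduced cycle, and 114% or 86% over two plus two full cycles, depending on a cycle length the SAP does not specify. If exposure ends at the last dose, the switch example becomes 133% or 100%, and a participant with no reduction who stops after one 2 on/1 off cycle shows 150%.

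These figures assume full compliance, on-schedule cycles and the dosing days implied by the schedule names. The size of the effect in the trial depends on how many participants change cycle length and how early they stop, which the documents cannot tell us.

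A reader might infer that dose selection is compromised. The documents do not support that. ADI and RDI are descriptive exposure outputs, and no DLT or escalation rule refers to them. DLT evaluability has its own criterion for the share of planned dose received in Cycle 1 (SAP 6.1). The correction is still worth making, because it changes reported values at almost no cost.

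**What to change.** In SAP 8.9.4 and 8.9.5:

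1. Define both quantities per week. ADI = cumulative dose / (exposure days / 7). PDI = initial total daily dose × planned dosing days per week of the starting regimen. RDI = ADI / PDI.
2. State that PDI stays on the starting regimen after any change of dose, frequency or schedule.
3. Define duration of exposure for dose intensity so that it includes the planned off period of the last cycle, separately from duration of treatment in SAP 8.9.1. State how a last cycle cut short during its dosing days, or by the data cutoff, is counted.
4. Write total daily dose explicitly. This only clarifies the wording for twice-daily dosing.

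The cost is SAP wording and one changed derivation, with no new data and no effect on participants. The downside is a unit less familiar to readers than mg/cycle.

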9. EFFICACY ANALYSIS

[figure not shown]

12.SAFETY ANALYSIS

12.1 Dose Limiting Toxicities

The number of DLTs will be summarized by treatment arms for the DLT Evaluable Population. A toxicity will be considered a DLT if it occurs from the first dose to the end of Cycle 1 (including the PK evaluation period), meets the pre-defined criteria for DLTs, is deemed at least possibly related to trial treatment, and is not clearly and incontrovertibly due to disease progression or extraneous cause. Toxicity will be assessed using CTCAE v 5.0, unless other specified. Details of DLTs will be listed.

DLTs will be defined as any of the following:

Any death not clearly due to the underlying disease or extraneous causes

Hematologic TEAES:

- Grade 4 neutropenia
- Febrile neutropenia (defined as absolute neutrophil count (ANC) <1000 cells/ μ L with a single temperature of 38.3°C [100.4°F] for > 1 hour).
- Grade 4 thrombocytopenia or Grade 3 thrombocytopenia associated with Grade \geq 2 bleeding.
- Grade 4 anemia or Grade 3 anemia requiring red blood cell (RBC) transfusion given to participants with documented anemia-related symptoms.

Non-Hematologic TEAEs:

- Any Grade \geq 3 TEAE except the below
 - 1. Grade ≥ 3 non-hematologic laboratory abnormalities that are asymptomatic and respond to medical intervention or resolve to grade 1 in \leq 72 hours.
 - 2. Grade 3 fatigue with duration < 7 days
 - 3. Grade \geq 3 nausea/vomiting/diarrhea that lasts \leq 72 hours and resolves with or without optimal supportive care.
 - 4. Grade \geq 3 amylase or lipase elevation not associated with symptoms or clinical manifestations of pancreatitis.
 - 5. The use of red blood cell transfusion for anemia Grade <3 or the use of G-CSF for Grade <4 neutropenia
- Symptomatic Grade ≥ 3 QTc prolongation (QTcF ≥ 501 msec on at least two separate electrocardiogram (ECGs)), or asymptomatic Grade ≥ 3 QTc prolongation that has been confirmed by repeat testing and reevaluation by a qualified person and persists after correction of reversible causes such as electrolyte abnormalities or hypoxia.
- Drug-induced liver injury meeting Hy's Law criteria defined as:
 - 1. ALT or AST ≥3-fold above the Upper Limit of Normal (ULN) or 5.0 x ULN in the case of liver metastases at baseline and
 - 2. Serum total bilirubin \geq 2-folde above ULN (without findings of cholestasis) and
 - 3. Alkaline phosphatase $\leq 2 \times ULN$ and
 - 4. No other overt reason for liver injury

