3. INTRODUCTION

This document describes the statistical methods to be implemented in the statistical analysis of data collected under clinical study Protocol RP-1664-01, titled: "Phase 1 Trial of the Safety, Pharmacokinetics (PK), Pharmacodynamics, and Preliminary Clinical Activity of RP-1664 in Participants with Advanced Solid Tumors". This Statistical Analysis Plan (SAP) contains definitions of analysis populations, derived variables, statistical methods for the analyses of baseline, efficacy, and safety data and the data listings and summary tables which will be produced. Details will be described to ensure the results are complete and appropriate to allow valid conclusion regarding the study objectives.

The analysis details for pharmacokinetic, pharmacodynamics, and biomarker analyses are not described within this SAP. A separate analysis plan may be implemented for those analyses.

This document has been prepared based on Protocol Version 3.0, dated March 24, 2025.

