4.1 Study Design

The trial will follow a Bayesian Optimal Interval (BOIN) design to guide escalation and de-escalation decision, establish a maximum tolerated dose (MTD), and identify a dose and schedule of RP-1664 that is tolerable.

All participants will undergo a PK evaluation period starting at Cycle 0 Day 1. Participants will be assigned to receive either a single dose of RP-1664 at the highest Safety Review Committee (SRC) approved dose level with PK collection over the subsequent 48 hours to characterize the half life (t1/2) of RP-1664 in the fasted state or enrolled into a cohort to investigate the effect of food on RP-1664 PK.

The starting dose (Dose Level 1) is 10 mg once daily (QD). RP-1664 will initially be given QD on a 2 weeks on 1 week off schedule to allow 1 week for bone marrow recovery.

The first escalation (Dose Level 2) will be up to 30 mg to limit the number of participants receiving a potentially subtherapeutic dose. After Dose Level 2, escalation will proceed with up to 100% increases in RP-1664 after evaluation of tolerability by the SRC until Dose Level S. Dose Level S is defined as the dose level at which any of the following safety signals occur during Cycle 0 or Cycle 1:

- Any \geq Grade 3 hematological toxicity
- >50% decrease in platelets or neutrophils from Cycle 0 Day 1
- >2 g/dL decrease in hemoglobin from Cycle 0 Day 1
- Any ≥ Grade 2 drug-related non-hematological toxicity lasting >5 days or requiring clinical intervention, except Grade 2 fatigue, nausea, vomiting, diarrhea, or constipation
- Any adverse event (AE) of any grade limiting tolerability as assessed by the SRC

At Dose Level S, the cohorts will be expanded to a minimum of 3 participants to further evaluate safety, PK, and pharmacological activity. Evidence of pharmacologic activity can include Grade ≥ 2 drug-related toxicity at any cycle, PK

data demonstrating exposure levels predicted to be efficacious based on nonclinical studies, or other evidence of treatment-related activity as agreed on by the SRC. Dose decisions will be based on assessments in 2 or more dose-limiting toxicity (DLT) evaluable participants completing the DLT evaluation period. Any escalation of RP-1664 after Dose Level S will be in increments up to 75% as agreed upon by the SRC and will enroll cohort sizes of $N \ge 3$.

RP-1664 Escalation Dose Level	Escalation Plan
	Daily (mg) or % of previous dose
	increment
1	10 mg
2	Up to 30 mg
3 to S	Up to 100% increases until Dose Level S

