6.1 DLT Evaluable Population

The DLT Evaluable Population will consist of participants who have met the minimum safety evaluation requirements of the trial and /or who experience a DLT at any time during the DLT evaluation period (from the start of treatment through the end of Cycle 1). Minimum safety requirements will be met if, during Cycle 1 of treatment, the participant receives at least 75% of their planned total dose of RP-1664, completes required safety evaluations, and is observed through the end of Cycle 1. This analysis set will be used for DLT analyses, unless otherwise specified.

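### SAP 12.1 prints two unequal temperatures as one febrile-neutropenia DLT threshold: 38.3°C is 100.9°F, whereas 100.4°F is 38.0°C

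*SAP*

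**What the plan says.** SAP section 12.1 lists the hematologic DLTs. One is "Grade 4 neutropenia", with no temperature condition. Another is febrile neutropenia, defined as an ANC below 1000 cells/µL "with a single temperature of 38.3°C [100.4°F] for > 1 hour". No inequality sign precedes the temperature.

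The same section sets the grading standard: "Toxicity will be assessed using CTCAE v 5.0, unless other specified". It also states the use of the list: "The number of DLTs will be summarized by treatment arms for the DLT Evaluable Population". A qualifying event must fall between the first dose and the end of Cycle 1, be at least possibly related to treatment, and not be clearly due to progression or another cause.

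SAP section 6.1 makes a participant DLT-evaluable by either of two routes. One is meeting minimum safety requirements, including that "the participant receives at least 75% of their planned total dose of RP-1664" in Cycle 1. The other covers those "who experience a DLT at any time during the DLT evaluation period".

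SAP section 4.1 says: "The trial will follow a Bayesian Optimal Interval (BOIN) design to guide escalation and de-escalation decision". SAP section 3 says: "This document has been prepared based on Protocol Version 3.0, dated March 24, 2025".

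**The concern.** A bracketed Fahrenheit value should be the conversion of the Celsius value beside it. Here it is not, so the criterion holds two thresholds. A participant with an ANC below 1000 but without Grade 4 neutropenia, and with a fever between the two, is a DLT on one figure and not on the other.

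The supplied text offers no way to choose. No other passage gives a fever threshold. The CTCAE v5.0 reference yields where something else is specified, and this line specifies its own definition. The missing inequality sign adds doubt at the boundary. Attaching a duration to a single temperature leaves it unclear whether one reading or a sustained fever is meant, although the literal wording requires the duration.

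At stake is the DLT table, in both numerator and denominator, because a participant below the 75% dose requirement is evaluable only through having had a DLT. The Protocol synopsis names neutropenia as an expected toxicity of this drug, so the criterion is not a remote one.

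**Working it through.** **Unit conversion.** Inputs: 38.3°C and 100.4°F, both from SAP 12.1.

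- °F = °C × 9/5 + 32: 38.3 × 9/5 + 32 = 68.94 + 32 = 100.94°F. The printed bracket is 100.4°F.
- °C = (°F − 32) × 5/9: (100.4 − 32) × 5/9 = 68.4 × 5/9 = 38.0°C. The printed value is 38.3°C.
- Difference: 38.3 − 38.0 = 0.3°C; 100.94 − 100.4 = 0.54°F.

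The printed equivalence does not reproduce. Rounding 100.94 to one decimal gives 100.9 and to a whole degree gives 101, never 100.4.

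**Discordant band**, reading each figure as a minimum:

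| Temperature | In °F | Meets 38.3°C | Meets 100.4°F |
|---|---|---|---|
| 37.9°C | 100.22 | no | no |
| 38.0°C | 100.40 | no | yes |
| 38.2°C | 100.76 | no | yes |
| 38.3°C | 100.94 | yes | yes |

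If the intended sign is strictly greater than, the band is instead above 38.0 up to and including 38.3°C.

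**Effect on the DLT table.** Take three treated participants, one in the band with all other conditions for this DLT met, and no other DLT.

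- All three meet the minimum safety requirements: 0/3 (0.0%) on the Celsius figure, 1/3 (33.3%) on the Fahrenheit figure.
- The participant in the band took less than 75% of the planned dose: 0/2 on the Celsius figure (not evaluable), 1/3 on the Fahrenheit figure (evaluable through the DLT).

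**Why start at three.** The general entry floor for ANC is 2000 cells/mm³ (Protocol synopsis, inclusion criterion 12c), and 50% of 2000 is 1000. An ANC below 1000 is therefore a fall of more than 50% from any Cycle 0 Day 1 value of 2000 or more. That triggers Dose Level S, where the cohort expands to at least 3. Neuroblastoma participants with marrow involvement have a lower floor, so this step need not apply to them.

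**Conditional effect on escalation.** This part assumes that the full protocol carries the same DLT wording. The BOIN target φ is not visible, so four values are shown, with the default φ₁ = 0.6φ and φ₂ = 1.4φ, also assumed:

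- Escalate if the DLT rate ≤ λe = ln[(1−φ₁)/(1−φ)] / ln[φ(1−φ₁)/(φ₁(1−φ))]
- De-escalate if the DLT rate ≥ λd = ln[(1−φ)/(1−φ₂)] / ln[φ₂(1−φ)/(φ(1−φ₂))]

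| Target φ | λe | λd | 0/2, 0/3, 0/6 | 1/3 (0.333) | 1/6 (0.167) |
|---|---|---|---|---|---|
| 20% | 0.1572 | 0.2385 | escalate | de-escalate | stay |
| 25% | 0.1968 | 0.2984 | escalate | de-escalate | escalate |
| 30% | 0.2365 | 0.3585 | escalate | stay | escalate |
| 33.3% (1/3) | 0.2630 | 0.3987 | escalate | stay | escalate |

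With three evaluable, one reclassified participant changes the decision at every target shown. With six, it does so only at 20%.

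**The case against.** The strongest reply is that this is a transcription slip with little reach. The bracket can be read as a bad conversion of the leading 38.3°C rather than as a rival criterion. To matter, a case needs an ANC below 1000 but not Grade 4, a fever inside a 0.3°C band for over an hour, possible relatedness, onset by the end of Cycle 1, and no other DLT. DLT status also involves judgement, and the SAP table may simply count events already called under the full protocol. The safety consequence is partly cushioned: for a participant who starts at 2000 or more, an ANC below 1000 triggers Dose Level S and caps later steps at 75%, whatever the temperature. The escalation figures rest on a target, boundaries and protocol wording that cannot be seen.

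Much of this stands as a limit on size. The frequency cannot be derived, any effect depends on a case arising, and the escalation table is illustrative and should not set the priority. None of it removes the defect. Taking 38.3°C as the intended value is a guess, and US sites could well apply the Fahrenheit figure. Dose Level S slows escalation but does not settle whether the event counts as a DLT. SAP 12.1 presents its list as the DLT definition, so that list needs one threshold.

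**Conclusion.** The concern holds, and the line should be fixed. The febrile-neutropenia DLT is wrong as written: its two temperatures differ by 0.3°C (0.54°F), and nothing supplied says which governs. The conversion needs no assumption. The band of 38.0 to below 38.3°C assumes that the figure is a minimum.

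Within the SAP, one participant in the band moves a three-participant cohort from 0% to 33.3% DLTs, or from 0/2 to 1/3 when evaluability depends on the event. Whether the error also reaches escalation depends on the DLT section of Protocol Version 3.0, which is not in the supplied text. The duration wording is a secondary ambiguity.

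**What to change.** In SAP 12.1:

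- Make the pair agree, as either 38.3°C [100.9°F] or 38.0°C [100.4°F], according to what the sponsor intended.
- State the inequality sign.
- State whether the one-hour duration qualifies the single temperature or belongs to a separate sustained-fever condition. If the sponsor confirms that two conditions were meant, one form is a single temperature >38.3°C [100.9°F], or ≥38.0°C [100.4°F] sustained for more than 1 hour. The supplied documents do not establish that intent.
- Align the line with the DLT definition in the full protocol, correcting that too if it carries the same pair.
- Re-check any febrile-neutropenia DLT calls and DLT-evaluable flags already set.

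The cost is one line of SAP text, one cross-check and a short review of existing calls. No procedures or participants are added.
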